Participants who experience a significant psychiatric or medical problem requiring an overnight hospitalization at an acute care facility will be considered to have experienced an SAE. In general, most SAEs will result in inpatient care and thus in transfer to the inpatient division of CMHC. All SAEs will result in the completion of an SAE Form and a verbal report within one hour to the Principal Investigator ([name]) and the clinic directors (Drs. [name], [name]). Within 24 hours, the following additional individuals will be informed: 1) all co-investigators; and 2) the DSMB. Adverse events that are serious and unanticipated and probably, possibly, or definitely related or adverse events occurring with greater frequency than anticipated will be reported to the Yale Human Investigation Committee within 48 hours of discovery. The procedures for SAE reporting include written documentation using the clinical notes related to the adverse event and specific forms detailing the event with a sign-off by all appropriate supervisory personnel. Communication of recommendations and decisions from all parties (DSMB, Yale Human Investigations Committee, and CMHC Administration) are made back to the investigator in a timely manner. We will report all protocol amendments or changes in the informed consent form to NIDA as well as any temporary or permanent suspension of patient accrual.

4. Confidentiality & Security of Data:

- a. What protected health information (medical information along with the HIPAA identifiers) about subjects will be collected and used for the research?

In Phase 1, no PHI will be collected. In Phase 2, PHI that will be collected includes names, addresses, phone numbers, and email addresses for locator purposes.

Our study assessments/forms have been designed to avoid collecting identifiable information (e.g., no PHI identifiers are collected on CRFs). The only dates collected are

protocol session dates. These are changed to 'number of sessions completed' when data sets are anonymized and released to other investigators.

b. How will the research data be collected, recorded and stored?

Research data are collected on CRFs, and sent to data managers in our research offices on a closed secure network. All computers used by research staff are password protected. No identifying information is on CRFs. Only authorized individuals will have access to CRFs.

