f. Who will have access to the protected health information (such as the research sponsor, the investigator, the research staff, all research monitors, FDA, QUACS, SSC, etc.)? (please distinguish between PHI and de-identified data)

The Yale PI and the research staff will have access to PHI and coded data. The funding agency, NIAAA, may access the data for routine audits.

g. If appropriate, has a [Certificate of Confidentiality](#) been obtained?

Applied for.

h. Are any of the study procedures likely to yield information subject to mandatory reporting requirements? (e.g. HIV testing – reporting of communicable diseases; parent interview - incidents of child abuse, elderly abuse, etc.). Please verify to whom such instances will need to be reported.

Limits to confidentiality include only disclosure of acute suicidality, homicidality, or abuse of a minor/elder, as is standard in clinical practice and indicated in the consent form. When there is reasonable cause to suspect or believe there is a case of child abuse or elder abuse, a report will be made to the CT Department of Children and Families (DCF) or CT Department of Social Services (DSS), Protective Services for the Elderly (PSE). Designated clinic personnel will be notified as per clinic policies.

6/29/2011 SECTION X: POTENTIAL BENEFITS

Potential Benefits: Identify any benefits that may be reasonably expected to result from the research, either to the subject(s) or to society at large. (Payment of subjects is not considered a benefit in this context of the risk benefit assessment.)

The major potential benefit in this study is in reduction of alcohol use via the study treatments, which may, in turn, foster improvement in participants' legal, medical, interpersonal, psychological and occupational functioning.

SECTION XI: RESEARCH ALTERNATIVES AND ECONOMIC CONSIDERATIONS

1. **Alternatives:** What other alternatives are available to the study subjects outside of the research?
Individuals who do not wish to participate or who are ineligible for the trial will be referred back to their clinician.
2. **Payments for Participation (Economic Considerations):** Describe any payments that will be made to subjects, the amount and schedule of payments, and the conditions for receiving this compensation.

Phase 1 (Development of the CBT modules, Years-1-2):

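### The only written SAE criterion is overnight hospitalisation, so a death or life-threatening event without admission is not assured prompt SAE reporting

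*Protocol*

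**What the plan says.** Protocol Section IX, item 3 says that participants with a significant psychiatric or medical problem "requiring an overnight hospitalization at an acute care facility will be considered to have experienced an SAE". It continues: "In general, most SAEs will result in inpatient care and thus in transfer to the inpatient division of CMHC".

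Three reporting steps follow in the same paragraph.

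- One hour: "All SAEs will result in the completion of an SAE Form and a verbal report within one hour to the Principal Investigator"; the clinic directors receive the same report.
- 24 hours: "Within 24 hours, the following additional individuals will be informed: 1) all co-investigators; and 2) the DSMB".
- 48 hours, to the Human Investigation Committee (HIC), on either of two grounds. The first is "Adverse events that are serious and unanticipated and probably, possibly, or definitely related". The second is "adverse events occurring with greater frequency than anticipated will be reported to the Yale Human Investigation Committee within 48 hours of discovery".

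The DSMB also receives a quarterly report. The numbered list in item 3 includes both AEs and SAEs among its contents. A later paragraph of the same item describes aggregate data, names serious adverse events but not other adverse events, and adds a general provision for any other helpful data.

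On a separate matter, the SAE paragraph ends by committing to report protocol amendments or "changes in the informed consent form to NIDA as well as any temporary or permanent suspension of patient accrual". Section IX, item 4.f states: "The funding agency, NIAAA, may access the data for routine audits".

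**The concern.** Staff who must report within an hour need a definition that tells them at once whether an event qualifies. This one turns on where and for how long the participant was treated. The gravest outcome, a death outside hospital, involves no overnight admission, and a suicide attempt or withdrawal seizure treated and released the same day does not either. The following sentence adds doubt: if admission is what makes an event an SAE, it is odd to say that most SAEs lead to inpatient care; if some SAEs do not, the protocol never describes them.

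The gap matters in this trial for three reasons, all from the Protocol. Section IX, item 3 gives the possible vulnerability of people with alcohol use as the reason for having a DSMB. Section V, item 3 allows applicants who are physically dependent to be rescreened after detoxification and follows participants for six months after treatment ends, and Section IX, item 4.h provides for disclosure of acute suicidality. Finally, Section IX, item 3 plans no interim review of safety data by arm, so prompt reporting of single events is a main safeguard, and it rests on this definition.

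**Working it through.** No calculation applies: the point depends on no sample size, error rate or event count. The check has three steps.

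**Step 1: look for any other seriousness criterion.** Section IX, item 3 supplies the hospitalisation criterion and nothing else. The assessment table in Section V, item 3 lists an SAE reporting form by name, with no criteria and no visit marked. The conflict-of-interest statement before Section II mentions a sponsor-initiated monitoring plan but quotes no definition from it. The SAP text covers treatment outcomes and attrition and does not mention adverse events. None of these adds death, a life-threatening event or any other grave event.

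**Step 2: trace a death or life-threatening event without overnight admission through each route.**

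| Route | Trigger as written | Recipient | Assured for this event? |
|---|---|---|---|
| SAE form and one-hour report | Event is an SAE | Investigator, clinic directors | No; the one written criterion is not met |
| 24-hour notice | Event is an SAE | Co-investigators, DSMB | No, same reason |
| 48-hour report, first ground | Serious, unanticipated and at least possibly related | HIC | Only if judged serious (a word not separately defined) and the other two conditions hold |
| 48-hour report, second ground | More frequent than anticipated | HIC | Only if so judged; does not depend on the SAE definition, but no anticipated rate is stated |
| Quarterly report | Periodic | DSMB | Counted among AEs under the numbered list; need not be itemised under the later description |

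The first two routes depend wholly on the definition. The third depends on it if the word serious takes the only meaning the protocol gives. The fourth is independent of it but conditional. The fifth is slow and aggregate.

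**Step 3: compare the timing.** For the DSMB, an event classed as an SAE is notified within 24 hours. An event not so classed is guaranteed to come up only at the next quarterly report, so the wait could be as long as one quarter. For the HIC, the time is 48 hours if either ground is met. For the investigator, no interval can be derived, because the protocol does not say when non-SAE events must be passed on.

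**The agency name.** The sentence on amendments and accrual suspensions names NIDA, while Section IX, item 4.f calls NIAAA the funding agency. The innovation part of Section V, item 2 also ties the project to NIAAA priorities. The two names do not match, and the documents do not explain the difference.

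**The case against.** The best reply is that the definition states a sufficient condition. It says that participants with an overnight admission count as having had an SAE; it does not say that only they do. The sentence about most SAEs fits that reading and suggests that the authors had a wider idea in mind. A reader might therefore go too far in inferring that the protocol rules deaths out by definition. It does not. What stands against the reply is that the wider idea is never written down, so the person deciding whether the one-hour report is due has one criterion to apply.

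A fuller definition may also exist on the SAE form or in the separate monitoring plan, neither of which is among the documents. That is possible, but the protocol neither repeats nor cites such a definition.

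The 48-hour HIC route also has real force. An unanticipated, possibly related death would plausibly be called serious in ordinary usage, so it is wrong to say that no expedited report could follow. The route is partial, though: its first ground requires relatedness and unexpectedness, its second has no stated benchmark, and it does not name the DSMB as a recipient.

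Finally, the protocol rates overall risk as minimal, and neither the primary outcome nor its analysis is touched. That limits the weight of the point without removing it.

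**Conclusion.** The concern holds as a gap in the written criteria. The SAE form, the one-hour report and the 24-hour DSMB notice are not assured for a death or life-threatening event without overnight admission; the HIC report is conditional, and the DSMB's fallback is the quarterly aggregate report. The number of events affected cannot be estimated because no rates are given. The conclusion assumes that staff apply the protocol text as it stands and that no wider definition governs from the SAE form or the separate monitoring plan.

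Three stronger readings are not supported. A reader might infer that a between-arm comparison of SAEs would turn into a comparison of admissions, but no such comparison is planned: the DSMB sees aggregate data, and the SAP text has no safety analysis. A reader might infer that the investigator would wait a quarter to learn of such an event, but nothing says so, and Section V, item 3 provides for weekly assessment and close monitoring during treatment. And a reader might conclude that NIDA is the wrong agency, or that NIAAA would not be told of a suspension. The funding details that would follow Section III, item 1 are not in the text available for review, so only the mismatch can be stated. It is minor and unrelated to the SAE definition.

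**What to change.** In Section IX, item 3, extend the definition so that death, a life-threatening event and any event of equal gravity count as SAEs whether or not the participant is admitted. Reword the sentence about most SAEs to agree with it. State that the word serious in the 48-hour HIC rule has the same meaning, and use the same definition on the SAE form and in the DSMB report. If the form or the separate monitoring plan already holds a fuller definition, bring it into the protocol or cite it there.

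Separately, reconcile the agency to be notified of amendments and accrual suspensions with the funding agency named in Section IX, item 4.f; the sponsor should confirm which is meant, or whether both are.

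The cost is a sentence or two in the protocol, matching text on one form and one report, and possibly a few more expedited reports. Sample size, outcomes and the efficacy analysis are unchanged.

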### **1. Determination of Treatment Outcomes**

*a. Data reduction:* Primary outcome variables have been defined *a priori* to reduce the risk of Type I error. Preparatory analyses include evaluation of baseline equivalence of treatment groups on demographic and prognostic variables and comparability of rates of data availability across conditions.

*b. Strategies for management of differential attrition:* Data analyses will be conducted on the intent-to-treat sample and we will attempt to follow all participants regardless of their retention in treatment. We have established our ability to contact and follow participants who drop out of treatment and to conduct true intent-to-treat analyses, including supplemental analyses that account for whether data was collected before or after dropout/withdrawal. While we anticipate that assertive efforts to locate and interview participants who drop out of treatment will result in low numbers of missing participants and minimal missing data in the final dataset, we will minimize the impact of missing data through the use of random effects regression modelling.

*c. Evaluation of treatment effects at posttreatment and follow-up:* The principal strategy for assessing the efficacy of the study treatments on outcome over time will be random effects regression models for continuously measured primary (e.g. percent days of abstinence by week) and secondary (e.g., acquisition of coping skills) outcome variables. The focus of the repeated measures analyses will be the 'contrast by time effects', which essentially evaluates whether the slopes, or rates of change, of one group differ from the slopes of another group. We have used these methods to evaluate main and interaction effects, with appropriate covariates (e.g., retention, compliance with treatment, time spent working with the CBT4CBT program) in multiple previous trials. Follow-up data will be analyzed using random-effects regression modeling for our primary outcome measures across time, using the contrasts described above, with appropriate covariates (e.g., length of time in treatment, exposure to other treatment during follow-up). Random effects regression models have several advantages in

follow-up data from clinical trials of substance users where participants are unlikely to attend follow-up evaluations precisely at the desired fixed points, and are less vulnerable than traditional MANOVA approaches to missing data. As in our previous trials , we estimate that our extensive efforts to track participants will yield a 90% follow-up rate.

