Human Investigation Committee Signature

This protocol is valid through

SECTION V: RESEARCH PLAN**1. Statement of Purpose:** State the scientific aim(s) of the study, or the hypotheses to be tested.

The goal of this project is to address a major challenge in health disparities as defined by NIH and the Institute of Medicine, specifically, the need for accessible, effective, evidence-based treatments for Latino/as.

Specific aims are as follows:

- To adapt our existing CBT4CBT program for use with Spanish-speaking alcohol users in a web-based platform
- To conduct an 8-week randomized trial evaluating the feasibility and efficacy of adding CBT4CBT-Spanish to treatment as usual in a community based treatment program in a population of 90 Spanish-speaking individuals who meet current criteria for alcohol use disorder
- To evaluate the long-term durability and/or delayed emergence of treatment effects through a six month follow-up after termination of the study treatments. Given previous evidence regarding the durability of standard clinician-delivered CBT₄₁ and computer-assisted CBT4CBT₂₅, we hypothesize that CBT4CBTSpanish will be significantly more effective than standard treatment alone through the follow-up.

2. Background: Describe the background information that led to the plan for this project.

Provide references to support the expectation of obtaining useful scientific data.

A Health disparities among Latinos, accessibility of evidence based therapies (EBTs).

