c. *Evaluation of treatment effects at posttreatment and follow-up*: The principal strategy for assessing the efficacy of the study treatments on outcome over time will be random effects regression models for continuously measured primary (e.g. percent days of abstinence by week) and secondary (e.g., acquisition of coping skills) outcome variables. The focus of the repeated measures analyses will be the 'contrast by time effects', which essentially evaluates whether the slopes, or rates of change, of one group differ from the slopes of another group. We have used these methods to evaluate main and interaction effects, with appropriate covariates (e.g., retention, compliance with treatment, time spent working with the CBT4CBT program) in multiple previous trials^{14, 151, 160, 200, 201, 254}. Follow-up data will be analyzed using random-effects regression modeling²⁵⁵ for our primary outcome measures across time, using the contrasts described above, with appropriate covariates (e.g., length of time in treatment, exposure to other treatment during follow-up). Random effects regression models have several advantages in follow-up data from clinical trials of substance users where participants are unlikely to attend follow-up evaluations precisely at the desired fixed points, and are less vulnerable than traditional MANOVA approaches to missing data^{208, 209, 251, 252}. As in our previous trials^{16, 126}, we estimate that our extensive efforts to track participants will yield a 90% follow-up rate.

d. *Adequacy of sample size*: This Stage 1 trial is intended to provide initial pilot testing and feasibility testing of the web-based CBT4CBT program in a Spanish-speaking sample of individuals with alcohol use disorder. Based on SSize software, the proposed sample sizes will enable us to detect effect sizes of .35 or higher for either hypothesis, which will be the criterion for determining whether CBT4CBT-Spanish-Alcohol has adequate promise to justify a fully powered randomized trial²⁵⁶. This sample size was sufficient for the English-language trials of the drug and alcohol versions of CBT4CBT, which yielded effect sizes of .46-.59^{13, 15, 16}.

Power calculations for random effects regression	Power	Estimated effect size	Estimated ICC	# of datapoints	Sample size per cell
H1: (CBt4CBT-S + ST) v ST, main effect for active treatment phase (assessed weekly, baseline-8weeks)	.80	.35	.40	9	45

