H2: (CBT4CBT-S + ST) vs ST, main effect for follow-up (assessed monthly, end of treatment-6 months)	.80	.50	.80	7	40

2. Treatment specificity and mediators

We will explore the extent to which participants improve coping skills over time using the ARRT as described above and the extent to which acquisition of coping skills may mediate outcome for CBT4CBT-Spanish-Alcohol in this sample. We have described our use of these models and strategies to evaluate treatment mediators in Preliminary Studies, above, and in several papers^{13, 105, 108, 151}. Following the general analytic framework outlined by Kraemer²⁵⁷, we will use the product of the coefficients method to evaluate the relationship between the mediator (e.g., acquisition of CBT-specific coping skills as measured by the ARRT), or indirect effect, and outcome^{155, 156, 258}. After running a regression equation to determine (1) the effect of treatment on the mediator (provides beta weight for a), we will evaluate (2) the strength of the relationship between the mediator, treatment, and outcome (provides beta b). Using MacKinnon's software PRODCLIN²⁵⁹, we will evaluate the asymmetric confidence intervals for the product of the regression estimates (a^*b).

SECTION VI: RESEARCH INVOLVING DRUGS, BIOLOGICS, PLACEBOS AND DEVICES

If this section (or one of its parts, A or B) is not applicable, state N/A and delete the rest of the section.

N/A

SECTION VII: HUMAN SUBJECTS

1. Subject Population:

Provide a detailed description of the types of human subjects who will be recruited into this study.

Participants will be individuals seeking outpatient treatment for alcohol use at the Connecticut Mental Health Center (CMHC), where the majority of clients are male (73%), middle aged (62%), unemployed (71%), unmarried (56%), and have not completed high school (64%). Spanish-speaking participants will be recruited from two CMHC outpatient programs (The Hispanic Clinic at [name] and the Substance Abuse Treatment Unit at [name]) or Connecticut Mental Health Center clinicians. Additionally, MAAS (The Multi- Cultural Ambulatory Addiction Service at [name]) has been appointed a recruitment site

2. Subject classification:

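### The SAP's focal contrast is a difference in slopes, but the power table and the third aim are about a difference in level; in the table's follow-up window, the slope does not test durability

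*SAP*

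**What the plan says.** SAP section 1, paragraph c (same text in Protocol V.5, paragraph 1.c) specifies random effects regression. It says "The focus of the repeated measures analyses will be the" contrast-by-time effect, and explains this as a comparison "which essentially evaluates whether the slopes, or rates of change, of one group differ from the slopes of another group". Follow-up is then modelled "for our primary outcome measures across time, using the contrasts described above". Main effects appear there only in a remark about earlier trials: "We have used these methods to evaluate main and interaction effects".

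The power table in Protocol V.5, paragraph 1.d labels H1 as "main effect for active treatment phase (assessed weekly, baseline-8weeks" (power .80, effect size .35, ICC .40, 9 data points, 45 per arm). It labels H2 as "main effect for follow-up (assessed monthly, end of treatment-6 months" (power .80, effect size .50, ICC .80, 7 data points, 40 per arm).

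The third specific aim (Protocol V.1) covers both durability and late emergence of effects. It hypothesises that the CBT4CBT arm "will be significantly more effective than standard treatment alone through the follow-up". Paragraph 1.d adds a progression rule: "the proposed sample sizes will enable us to detect effect sizes of .35 or higher for either hypothesis, which will be the criterion" for moving to a fully powered trial.

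**The concern.** A slope contrast and a level contrast answer different questions. The aim's hypothesis and the H2 label concern level: is the CBT4CBT arm better during follow-up? The SAP's focal contrast concerns change: is the gap widening or narrowing? Two parallel lines half a standard deviation apart show perfect durability and no slope difference.

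Someone who follows SAP 1.c literally in the table's follow-up window would therefore have no test of durability. A gap that narrows but still favours CBT4CBT at every visit would yield an unfavourable slope. The stated power would belong to a contrast other than the focal one. The .35 progression effect size (the H2 row itself uses .50) could be computed on either contrast, so the same data could meet it on one and miss it on the other.

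**Working it through.** **Assumptions.** Unit variance, compound symmetry, normal approximation, alpha .05 (none stated), two-sided unless noted. Effect sizes, ICCs, numbers of points and arm sizes come from the power table. Protocol section e (Follow-up) sets visits at 1, 3 and 6 months, whereas the table assumes 7 monthly points, so both grids are shown. Random-slope variance (.005 to .01 per month squared) and baseline correlations are my assumptions.

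**1. Reproducing the table as a main effect.** The variance of a subject's mean is (1+(m−1)ICC)/m, and SE = √(2 × variance/n).
- H2: (1+6×.80)/7 = .829; SE = √(2×.829/40) = .204; .50/.204 = 2.46. Power is .69 two-sided, .79 one-sided.
- H1: (1+8×.40)/9 = .467; SE = √(2×.467/45) = .144; .35/.144 = 2.43. Power is .68 two-sided, .78 one-sided.

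The table is approximately reproduced as a time-averaged difference at one-sided .05, and not at two-sided .05.

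**2. H2 as a slope, end of treatment to month 6.** The slope difference is Σ(t−t̄)δ(t)/Sxx. Its SE is √(2[(1−ICC)/Sxx + v]/n), where v is the random-slope variance. Sxx is 28 for months 0 to 6 and 21 for months 0, 1, 3, 6. With v = 0 the SEs are .0189 and .0218.
- Constant gap of any size: Σ(t−t̄)δ = 0, so rejection is .05 for any n, ICC or visit grid. Simulation gave .046 to .052.
- Other patterns:

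| Gap over 6 months | Monthly, v=0 | Months 0, 1, 3, 6, v=0 | Monthly, v=.005 / .01 |
|---|---|---|---|
| Emerges, 0 to .50 SD (slope .0833) | .99 | .97 | .92 / .81 |
| Fades, .50 to .25 SD (slope −.0417) | .60 | .48 | .39 / .30 |

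The fading rejections are against CBT4CBT. On the four-visit grid with v = .005 / .01, the SEs are .0270 and .0312, giving .34 / .27 for fading and .87 / .76 for emergence.

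**3. Slope fitted from baseline.** Times are weeks 0 to 8, then follow-up months of 4.345 weeks; n = 40; a .50 SD benefit is retained to month 6. Ranges run from ICC .40 to .80.

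| Benefit arises | Monthly follow-up | Months 1, 3, 6 |
|---|---|---|
| Complete by week 1 | .13 to .29 | .12 to .26 |
| Linear to week 8 | .83 to >.99 | .71 to .99 |

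This version depends on how quickly the benefit arose during treatment, so it does not isolate durability.

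**4. H1 as a slope.** Sxx = 60; SE = √(2×.60/(60×45)) = .0211.
- .35 SD step from week 1, held: slope 4×.35/60 = .0233; ratio 1.11; power .20.
- Linear growth to .35 SD: slope .35/8 = .0438; ratio 2.08; power .55.
- Power .80 needs linear divergence to 2.80×.0211×8 = .47 SD at week 8.

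**5. The proposed H2 test.** With baseline as covariate at correlation r with each follow-up value, the variance becomes .829 − r².

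| r | SE | Constant .50 SD | Emergence 0 to .50 (mean .25) |
|---|---|---|---|
| 0 | .204 | .69 | .23 |
| .4 | .183 | .78 | .28 |
| .6 | .153 | .90 | .37 |

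**The case against.** The plan does point to a contrast. The labels H1 and H2 occur only in the power table, and there each is a main effect. With the third aim's wording, that favours a level comparison. A model with arm, time and arm-by-time terms can supply a level contrast, and the remark about earlier trials shows the team knows both. This stands: the fault is a conflict between passages, not an unusable model or a complete absence of designation.

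The loss of durability also requires joining the SAP's slope to the table's window. The SAP gives no window, and the table, which does, calls its test a main effect. This stands too, so the consequence must be stated conditionally. Starting at baseline does not remove it, however, as step 3 shows.

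Three stronger readings are tempting and are not supported:
- That the trial cannot test durability. Nothing excludes a level contrast.
- That a fading benefit would probably be declared a negative result. The .60 holds only for two-sided testing on monthly points without random slopes. Otherwise it is roughly .3 to .5, and a one-sided test in favour of CBT4CBT would almost never reject.
- That a non-significant slope would block progression. The rule in paragraph 1.d is an effect size of .35, not a significance test, in a Stage 1 trial meant for piloting and feasibility.

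The slope is also the right tool for delayed emergence, and a conventional choice for H1. Neither point settles which contrast decides H2.

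**Conclusion.** The concern holds as an inconsistency that should be fixed. SAP 1.c makes the slope focal and extends it to follow-up; the power table and third aim concern level; no passage reconciles them.

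If the slope is H2's test in the table's window, durability is untested. That is algebra and needs no assumption about variance, sample size or visits. The other figures rest on alpha .05, compound symmetry and the assumed random-slope variances and benefit patterns. The slope's power for a retained benefit when fitted from baseline, about .12 to above .99, is too pattern-dependent to serve as a durability test. The stated .80 describes a time-averaged main effect at about one-sided .05; it does not describe the focal slope.

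**What to change.** - **H2:** pre-specify the time-averaged between-arm difference in percent days abstinent from end of treatment to month 6, adjusted for baseline, as the durability test. Keep arm-by-time as a supportive contrast, its sign read as fading or delayed emergence. A month-6 difference would also be a level test, but its power would need its own calculation.
- **H1:** either contrast is defensible; name one.
- **Both:** state the time origin, alpha and sidedness, recompute each power row for the named contrast, and say on which contrast the .35 progression effect size is judged.

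This costs SAP text and two re-run power rows. No visits or data are added: the Timeline Follow-Back at screening supplies the baseline value.

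There are two downsides. The average is weak for late emergence (.23 unadjusted, .28 to .37 at baseline correlations of .4 to .6), a case the supportive slope covers. And the restated unadjusted two-sided H2 power is .69; reaching .80 would need 2.80×.204 = .57 SD, or about 52 per arm. Adjustment raises it to .78 to .90 at those correlations, which the documents do not give, so the recomputed row should show a range.
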